6.2.3 Management of non-infectious pneumonitis

Both asymptomatic radiological changes (grade 1) and symptomatic non-infectious pneumonitis (grade 2 = not interfering with activities of daily living or grade 3 = interfering with activities of daily living and oxygen indicated) have been noted in patients receiving everolimus therapy. Non-infectious pneumonitis has been associated with everolimus and other mTOR inhibitors (Atkins 2004). In order to monitor for asymptomatic (grade 1) pulmonary infiltrates, a chest X-ray is required if a CT scan of chest is not used for bi-monthly disease evaluations. Additional chest CT scans may be performed, when clinically necessary. If noninfectious pneumonitis develops, a consultation with a pulmonologist should be considered. If the patient develops grade 3 pneumonitis, treatment with everolimus should be interrupted and the patient should be treated as medically indicated (short course corticosteroids, oxygen, etc). Management of non-infectious pneumonitis suspected to be associated with everolimus and dose modifications instructions are provided in Table 6.2.3.

Table 6.2.3 Management of non-infectious pneumonitis

Worst grade pneumonitis	Suggested investigations	Management of pneumonitis	everolimus dose adjustment
Grade 1	CT scans with lung windows and pulmonary function testing including: spirometry, DLCO, and room air O ₂ saturation at rest. Repeat chest x-ray/CT scan every 2 Cycles until return to baseline.	No specific therapy is required	No dose adjustment required for Pazopanib or everolimus. Initiate appropriate monitoring.
Grade 2	CT scan with lung windows. Consider pulmonary function testing includes: spirometry, DLCO, and room air O ₂ saturation at rest. Consider a bronchoscopy with biopsy and/or BAL. Monitoring at each visit until return to ≤ grade 1 or baseline. Return to initial monitoring frequency if no recurrence.	Symptomatic only. Consider corticosteroids and/or other supportive therapy if symptoms are troublesome.	Rule out infection and consider interruption of everolimus (and optional pazopanib) until symptoms improve to Grade ≤ 1. Re-initiate everolimus at one dose level lower. Discontinue everolimus if failure to recover within ≤ 28 days. Pazopanib may resume at the discretion of the treating physician and principal investigator once toxicity is recovered to ≤ Grade 1 even if everolimus is discontinued.

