6.3 Dose Modifications/Delays

6.3.1 General dose modification/Delays

Dose modifications for toxicities not otherwise covered in section 6.2 are listed in the table below. Patients who do not recover to grade 2 or less toxicity within 28 days will be removed from protocol therapy except where noted (ie. pneumonitis). In addition, patients may hold study intervention (pazopanib and everolimus) for greater than 28 days if the patient's physician and the overall principal investigator, [name], agree that the patient is deriving clinical benefit from the study drugs. Dose modifications for specific toxicities are covered in sections 6.2 and 6.3.

All toxicities, both during the DLT period and after it has been completed, will follow the guidelines laid out here in sections 6.2 and 6.3.

For definition of a Dose Limiting Toxicity, refer back to section 5.4.

Non-hematological toxicity

Toxicity	Actions
Non-Infectious Pneumonitis	Please refer to section 6.2.3
Reactivation of HBV or HCV flare	Please refer to section 6.2.4
Non-hematological toxicity Grade 2 (except pneumonitis – refer to section 6.2.3) (except hypertension, proteinuria, venous or arterial thrombosis, QTc prolongation- refer to section 6.3.2) (except hepatotoxicity – refer to section 6.3.3) (except elevated amylase and lipase- refer to section 6.3.5)	If the toxicity is tolerable to the patient, maintain the same dose. If the toxicity is “intolerable” to patient, interrupt pazopanib and everolimus until recovery to grade ≤ 1 . Then reintroduce pazopanib and everolimus at same dose. If event returns to “intolerable” grade 2, then interrupt pazopanib and everolimus until recovery to grade ≤ 1 . Then reintroduce pazopanib and everolimus at one dose level lower. If event is recurrent “intolerable” grade 2 despite two dose reductions, discontinue pazopanib and everolimus.
Grade 3 or 4 (except hyperlipidemia ¹) (except pneumonitis – refer to section 6.2.3) (except hypertension, proteinuria, venous or arterial thrombosis, QTc prolongation- refer to section 6.3.2) (except hepatotoxicity – refer to section 6.3.3)	Interrupt pazopanib and everolimus until recovery to grade ≤ 1 . Then reintroduce pazopanib and everolimus at one dose level lower. No more than 2 dose reductions allowed.
Stomatitis / oral mucositis / mouth ulcers	See section 6.2.3 Management of stomatitis / oral mucositis / mouth ulcers

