Recurrence of grade 3 toxicity after dose reduction	Reduce dose to the next lower dose level, if available. The lowest possible dose level of everolimus is 5 mg every other day (2.5 mg daily). Below this level, everolimus must be discontinued.
	Interrupt everolimus administration until resolution to \leq grade 1 or baseline

Intolerable grade 2 mucositis, or grade 3 AE, except hyperglycemia or hypertriglyceridemia or hypercholesterolemia (see Section 6.2.2.)	
grade / value.
 
If resolution occurs within \leq 7 days, everolimus should be re-started at the dose level prior to interruption.
 
If resolution takes $>$ 7 days, or if event recurs within 28 days, hold everolimus until recovery to \leq grade 1 or baseline grade / value and reintroduce everolimus at one dose level lower, if available.
 
Patients will be withdrawn from the study if they fail to recover to \leq grade 1 or baseline grade / value within 28 days.

Any other grade 4	
Hold everolimus until recovery to grade \leq 1 or baseline value
 
Reintroduce everolimus at one dose level lower, if available.

Grade 3 or 4 clinical liver failure (asterixis or encephalopathy/coma)	
Discontinue everolimus and Pazopanib

Recurrence of intolerable grade 2 mucositis or grade 3 event after dose reduction	
Reduce dose to the next lower dose level, if available. The lowest possible dose level of everolimus is 2.5 mg daily. Below this level, everolimus must be discontinued. If toxicity recurs at Grade 3, consider discontinuation.

Recurrence of grade 4 after dose reduction	
Discontinue everolimus and Pazopanib

Any non-hematologic toxicity requiring everolimus interruption for $>$ 28 days	
Discontinue everolimus and Pazopanib

¹Grade 3 hyperlipidemia (hypercholesterolemia and/or hypertriglyceridemia) should be managed using medical therapies without dose reduction (see Section 6.2.2).

Hematological toxicity

Grade 2 Thrombocytopenia (platelets $<75 - 50 \times 10^9/L$)	
Interrupt pazopanib and everolimus until recovery to grade \leq 1 ($\geq 75 \times 10^9/L$). Then reintroduce pazopanib and everolimus at initial dose. If thrombocytopenia again returns to grade 2, interrupt pazopanib and everolimus until recovery to grade \leq 1. Then reintroduce everolimus at one dose level lower. No more than two dose reductions are allowed.

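### Section 6.3.1 omits pazopanib's restart after recurrent grade 2 thrombocytopenia, gives two rules for one grade 3 event, and, with 6.3.2, relies on second reductions that the expansion cohort lacks

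*Combined protocol and SAP*

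**What the plan says.** Section 6 sets the number of reductions by starting level: one at levels -1 and 0, two at +1, +2 and +2A. All expansion patients start at level -1, pazopanib 400 mg and everolimus 5 mg daily (Section 5.1, Table 6). Table 6 gives one lower step: pazopanib 200 mg daily with everolimus 5 mg every other day. A patient who needs more stops, except that a patient who is benefiting may continue on one agent after discussion with the overall PI.

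**Thrombocytopenia (6.3.1).** After a first grade 2 episode both drugs restart at the initial dose. For recurrence the row reads "If thrombocytopenia again returns to grade 2, interrupt pazopanib and everolimus until recovery to grade" 1 or below, and then "Then reintroduce everolimus at one dose level lower. No more than two dose reductions are allowed".

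**Non-hematological events (6.3.1).** The grade 2 row, on recurrence, says "Then reintroduce pazopanib and everolimus at one dose level lower. If event is recurrent"; its last step is "grade 2 despite two dose reductions, discontinue pazopanib and everolimus". The grade 3 or 4 row holds both drugs, and then "Then reintroduce pazopanib and everolimus at one dose level lower. No more than 2 dose reductions allowed". A later row in the same table, labeled "Intolerable grade 2 mucositis, or grade 3 AE, except hyperglycemia or hypertriglyceridemia or hypercholesterolemia", holds everolimus only. It restarts everolimus at the previous dose if the event clears within 7 days, and one level lower if it takes longer or recurs within 28 days. The row for other grade 4 events holds everolimus and restarts it one level lower. Neither of these two rows mentions pazopanib.

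**Stomatitis (6.3.1).** The row says "See section 6.2.3 Management of stomatitis / oral mucositis / mouth ulcers", but the section with that number is "6.2.3 Management of non-infectious pneumonitis". Stomatitis is in 6.2.1.

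**Proteinuria (6.3.2).** Both drugs are held and restarted one level lower (Steps 1 and 2). Those steps are repeated at the first recurrence (Step 3). Treatment stops if the event recurs after two reductions (Step 4).

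**The concern.** These tables tell a site what to give a patient after toxicity. In three places they leave a held drug without a restart, give two answers for one event, or call for a dose that does not exist for the cohort now enrolling. The expansion cohort runs at two centers and safety is a secondary objective (Section 1.3.2). Two investigators who both follow the text could therefore dose the same event differently, and the toxicity summary would mix the results.

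**Working it through.** The plan gives no figure to reproduce. The check is a side-by-side reading, with simple dose arithmetic for size.

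**1. Which drugs restart after both are held**

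| Rule in 6.3.1 | Drugs named at restart |
|---|---|
| Grade 2 thrombocytopenia, first episode | both |
| Grade 2 thrombocytopenia, recurrence | everolimus only |
| Grade 3-4 thrombocytopenia | both |
| Grade 3 neutropenia | both |
| Grade 4 neutropenia | both |
| Grade 3 febrile neutropenia | both |
| Non-hematological grade 2 | both |

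The recurrence sentence is the only exception. For a level -1 patient, per 28-day cycle:

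- Pazopanib: 400 × 28 = 11,200 mg, or 200 × 28 = 5,600 mg (50%), or none.
- Everolimus: 5 × 28 = 140 mg at full dose; one level lower, 5 × 14 = 70 mg (50%).

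**2. Two rules for one non-hematological event**

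| Event not covered elsewhere | Grade 3 or 4 row | Later everolimus rows |
|---|---|---|
| Grade 3, clears within 7 days | both held; both restart one level lower (50% of each) | everolimus held; restarts at 100%; pazopanib not mentioned |
| Other grade 4 | both held; both restart one level lower | everolimus held; restarts one level lower; pazopanib not mentioned |

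For grade 3 the everolimus instructions are incompatible: 70 mg against 140 mg per cycle. For grade 4 the everolimus step agrees, and the rows differ only in whether they address pazopanib.

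**3. Number of reductions at level -1**

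Section 6 allows one, and Table 6 defines one lower step. Six rules refer to two reductions:

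- Directs a second reduction: proteinuria, Step 3. After one reduction the patient is at 200 mg daily and 5 mg every other day. Step 3 asks for a further level, which Table 6 does not contain, while Section 6 says stop.
- Discontinues only after two: non-hematological grade 2, grade 3 neutropenia, grade 4 neutropenia. At level -1 that trigger cannot be reached within Table 6.
- States a ceiling of two: non-hematological grade 3-4, grade 2 thrombocytopenia. A limit of one also satisfies a ceiling of two.

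**4. How often.** The phase I toxicity table in Section 2.3 shows thrombocytopenia in 5 of 9 patients (three grade 1, one grade 2, one grade 3), across two dose levels. The text beside it reports grade 3 rash, pruritus, diarrhea, pneumonia and pneumothorax. These events do occur with this combination, but no recurrence rate is given, so a count of affected patients would be a guess.

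**The case against.** Several points on the other side have force.

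- **Restart of pazopanib.** A dose level in this protocol is a pair of doses, and an interruption until recovery ends on recovery. One level below -1 is then 200 mg with 5 mg every other day. That is the most sensible reading, but the sentence names one drug where the sentence just before it names two, so a site could reasonably read it otherwise.
- **Two reductions.** A reader might infer that all six rules contradict Section 6. They do not. The tables serve every dose level, two is right for +1, +2 and +2A, and Section 6 ties the number to the starting level. The two ceilings are merely loose for this cohort. The objection does not answer proteinuria Step 3, which orders a second reduction, or fully answer the three rules that make two reductions the trigger for stopping.
- **Grade 4 events.** A reader might infer that pazopanib may continue unchanged through a grade 4 event. Silence in one row does not cancel the explicit hold in the other. What stands is that the rows should match.
- **Stomatitis.** Section 6.3.1 opens by limiting itself to toxicities not covered in 6.2, which favors 6.2.1, and the wrong cross-reference prints the right title. But the note closing 6.2.1 sends reductions back to 6.3.1, where the mucositis row can restart everolimus at the same dose after grade 3, while 6.2.1 restarts it lower.
- **Counting single-drug reductions.** A reader might infer that the plan leaves open whether an everolimus-only reduction uses up the one allowed. Section 6 does not restrict its limit to paired reductions, so its natural reading already counts it.

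The monthly calls between centers (Section 12.2) may limit divergence. They do not supply the missing rule.

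**Conclusion.** The point holds in three parts: an unstated pazopanib restart after recurrent grade 2 thrombocytopenia; incompatible instructions for a grade 3 non-hematological event that clears within 7 days; and a second reduction directed or presupposed by four rules where level -1 has only one. For an affected patient the pazopanib restart differs twofold, or is absent; in the grade 3 case everolimus differs twofold, and pazopanib is either halved or given no instruction. This rests on the expansion cohort starting at level -1, as Section 6 states, and on no precedence rule standing elsewhere; none was found.

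A reader might also infer damage to the efficacy test. The documents do not support that: the first-stage rule, the final cutoff and their stated error rates do not depend on these rows. This is inconsistent drafting of dosing rules and should be corrected for safety and consistent conduct.

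**What to change.** 1. In the grade 2 thrombocytopenia recurrence step, state that both drugs restart at the next level down in the patient's table (Table 6 for the expansion cohort: 200 mg daily and 5 mg every other day).
2. In all six rules, replace two with the number of reductions allowed for the starting level, one at level -1. Make proteinuria Step 3 conditional on a further level being available. At level -1, recurrence after the one reduction then means stopping, subject to the single-agent clause in Section 6.
3. Keep the 6.3.1 grade 3 or 4 row, acting on both drugs, as the one residual rule. Limit it to events not covered in 6.2 (including stomatitis in 6.2.1 and metabolic events in 6.2.2), 6.3.2 (including hemorrhage), 6.3.3 or 6.3.4. These limits matter. Without them the row would override continuation at the same dose for asymptomatic grade 3 amylase or lipase elevation, discontinuation for grade 3-4 hemorrhage, and the everolimus-only handling of metabolic events. The liver-failure row stays.
4. Delete the everolimus-only rows for grade 3 and other grade 4 events, or make them match that rule, and let 6.2.1 govern mucositis.
5. Correct the stomatitis cross-reference to 6.2.1. At the same time reconcile the 6.3.1 footnote (no dose reduction for grade 3 hyperlipidemia) with 6.2.2, which restarts everolimus lower after grade 3 metabolic events.

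A separate rule for counting single-drug reductions is not required. The cost is an amendment to table wording, with no new procedures or patients.

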6.3.3 Dose Interruptions/Modifications for Hepatotoxicity

Recommendations for everolimus and pazopanib dose interruptions/modifications in case of liver-related treatment-emergent AEs are provided below. As a general rule, since many subjects are taking multiple concurrent medications, it is critical to (a) do a thorough evaluation of the subject's concurrent medications, and (b) identify and discontinue those with known hepatotoxicity and replace with a non-hepatotoxic equivalent for the same indication if necessary.

Event	Dose Modification Algorithms
(A). ALT of $\leq 3.0 \times$ upper limit of normal (ULN)	Continue pazopanib and everolimus at current dose with full panel liver function tests (LFTs) ³ monitored as per protocol.
(B). ALT $>3.0 \times$ ULN to $\leq 8.0 \times$ ULN without bilirubin elevation (defined as total bilirubin $<2.0 \times$ ULN or direct bilirubin $\leq 35\%$) and without hypersensitivity symptoms (e.g., fever, rash) ²	
1. Continue everolimus and pazopanib at current dose.2. Perform the following assessments for excluding hypersensitivity and other contributing factors:
• Eosinophil count• Viral serology for hepatitis A, B and C• Liver imaging3. Monitor subject closely for clinical signs and symptoms; perform full panel LFTs weekly or more frequently if clinically indicated until alanine aminotransferase (ALT)/aspartate aminotransferase (AST) reduced to Grade 1.
(C). ALT $>8.0 \times$ ULN without bilirubin elevation (defined as total bilirubin $<2.0 \times$ ULN or direct bilirubin $\leq 35\%$) and without hypersensitivity symptoms (e.g., fever, rash) ²	
1st occurrence
 
Interrupt everolimus and pazopanib until toxicity resolves to \leq Grade 1 or baseline
 
2. Perform the following assessments for excluding hypersensitivity and other contributing factors:
• Eosinophil count• Viral serology for hepatitis A, B, C and E, cytomegalovirus, Epstein-Barr virus IgM antibody, or heterophile antibody, or monospot testing)• Liver imaging3. Monitor subject closely for clinical signs and symptoms; perform full panel LFTs weekly or more frequently if clinically indicated until alanine aminotransferase (ALT)/aspartate aminotransferase (AST) reduced to Grade 1. 
• * If the potential benefit for reinitiating pazopanib treatment is considered to outweigh the risk for hepatotoxicity, then reintroduce pazopanib at a reduced dose and measure serum liver tests weekly for 8 weeks. Re-challenge may be considered if ALL following criteria are met:
 
• ALT/AST reduced to Grade 1• Total bilirubin $<1.5 \times$ ULN or direct bilirubin $\leq 35\%$• No hypersensitivity signs or symptoms• Subject is benefiting from therapy. 
• Pazopanib and everolimus will be decreased by one dose level if treatment resumes.
 
• If AST or ALT elevation is $> 20 \times$ ULN, everolimus should be discontinued if resolution takes > 7 days
 
Recurrence

Event	Dose Modification Algorithms
	
Discontinue everolimus and pazopanib permanently and monitor subject closely for clinical signs and symptoms; perform full panel LFTs weekly or more frequently if clinically indicated.


(D). ALT >3.0 x ULN with concomitant elevation in bilirubin (defined as total bilirubin \geq2.0 x ULN; with direct bilirubin >35%) or with hypersensitivity symptoms (e.g., fever, rash).
	
 1. Discontinue everolimus and pazopanib immediately 2. Consult a gastroenterologist / hepatologist and perform the following assessments to identify potential co-factors: 
 • Eosinophil count • Viral serology for hepatitis A, B, C and E, cytomegalovirus, Epstein-Barr virus IgM antibody, or heterophile antibody, or monospot testing • Anti-nuclear antibody, anti-smooth muscle antibody, anti-mitochondrial antibody • Serum creatinine phosphokinase for possible muscle injury caused LFT elevation • Liver imaging (ultrasound or CT scan) 3. Monitor subject closely for clinical signs and symptoms; perform full panel LFTs weekly or more frequently if clinically indicated until LFTs reduced to Grade 1. 
If everolimus

For isolated total bilirubin elevation without concurrent ALT increases (defined as ALT < 3 X ULN)
	
 1. Isolated hyperbilirubinemia (ie in the absence of elevated ALT or other signs/symptoms of liver injury) does not require dose modification. Pazopanib inhibits UGT1A1 and OATP1B1, which can cause elevation of indirect (unconjugated) bilirubin in the absence of liver injury. 2. If bilirubin is > 1.5 x ULN in the absence of ALT elevation, fractionation of bilirubin elevation should be performed. If the bilirubin is predominantly indirect (unconjugated), continue everolimus and pazopanib at the same dose. If bilirubin is >35% direct (conjugated), stop everolimus and pazopanib and further evaluation for underlying cause of cholestasis should be performed. 3. If the subject is benefiting from the study treatment, contact Principal Investigator for possible re-challenge. Re-treatment may be considered if ALL following criteria are met: 
 • ALT < 3X ULN • Total bilirubin <1.5 x ULN or direct bilirubin \leq35% • No hypersensitivity signs or symptoms • Subject is benefiting from therapy. 
Pazopanib and everolimus will be decreased by one dose level if treatment resumes.

a. ³Full panel LFTs include: AST, ALT, alkaline phosphatase, γ -GT (GGT) and total bilirubin.

²Should HCV flare be confirmed, the guidelines for flare must take precedence (See section 6.2.4)

* Please refer to the Pazopanib Investigator's Brochure, Summary of Data and Guidance for Investigator, Warnings and Precautions, Hepatic Effects for information about rechallenge dose

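### Section 6.3.3: for a mainly direct bilirubin rise of more than 1.5 but less than 2.0 × ULN, both drugs stop at ALT below 3 × ULN but continue at current dose at ALT above 3 and up to 8 × ULN

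*Combined protocol and SAP*

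**What the plan says.** All the rules are in the table of section 6.3.3. Multiples below are of the ULN.

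- **Row (A), ALT up to 3.0.** Continue both drugs. The row has no bilirubin condition.
- **Row (B), ALT above 3.0 and up to 8.0, no hypersensitivity symptoms.** Its bilirubin condition begins "without bilirubin elevation (defined as total bilirubin" and gives two limbs joined by *or*: total below 2.0, or direct at most 35%. The action is "Continue everolimus and pazopanib at current dose", with eosinophil count, viral serology, liver imaging and at least weekly full-panel liver tests.
- **Row (C), ALT above 8.0, same bilirubin condition.** "Interrupt everolimus and pazopanib until toxicity resolves to" grade 1 or baseline.
- **Row (D), ALT above 3.0** with total bilirubin at least 2.0 and direct above 35%, or with hypersensitivity symptoms. Discontinue both drugs.
- **Isolated-bilirubin row,** with no concurrent ALT increase, "defined as ALT < 3 X ULN". Item 1 says that isolated hyperbilirubinemia needs no dose change. Item 2 says "If bilirubin is > 1.5 x ULN in the absence of ALT elevation, fractionation of bilirubin elevation should be performed"; a predominantly indirect rise continues, but "If bilirubin is >35% direct (conjugated), stop everolimus and pazopanib" and look for a cause of cholestasis. After re-challenge, "Pazopanib and everolimus will be decreased by one dose level if treatment resumes".

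The footnote that defines the full liver panel lists AST, ALT, alkaline phosphatase, GGT and total bilirubin, but not direct bilirubin.

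**The concern.** A hepatotoxicity rule should not become more permissive as liver injury increases. Here two rows use different bilirubin thresholds, 1.5 and 2.0, on either side of ALT 3. In the band between those thresholds, the patient with the higher ALT gets the weaker dosing action and is not sent for the test that decides the action at lower ALT.

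The protocol gives no reason for this. Its explanation for tolerating raised bilirubin is that pazopanib inhibits UGT1A1 and OATP1B1 and so raises indirect bilirubin without liver injury. That does not cover a mainly direct rise with raised ALT. What is at stake is the safety of an individual patient who stays on full doses of both drugs. Section 2.1.1.4 puts everolimus clearance at about half of normal in mild to moderate hepatic impairment.

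**Working it through.** No figure in the plan is in question, so the check applies the rows as written, assuming no hypersensitivity symptoms. Where the isolated-bilirubin row and row (A) overlap, item 2 of the former is read as governing over its item 1 and over row (A). Otherwise item 2 would have no effect.

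**Step 1. Two worked patients, direct fraction 60%.**

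| ALT (× ULN) | Total bilirubin 1.8 | Total bilirubin 2.5 |
|---|---|---|
| 2.9 | stop (isolated row) | stop (isolated row) |
| 3.0 | continue (row A only) | continue (row A only) |
| 3.1 to 8.0 | continue (row B) | discontinue (row D) |
| above 8.0 | interrupt (row C) | discontinue (row D) |

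At 1.8 the sequence is stop, continue, interrupt. It also runs backwards in recovery: if ALT falls from 5 to 2.5 with bilirubin unchanged, the instruction changes from continue to stop. At 2.5 the order is correct except at ALT exactly 3.0, which row (A) includes and the isolated row excludes.

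**Step 2. Where the reversal lies.** The actions were ranked continue < stop or interrupt < discontinue over 9 total-bilirubin values (1.0, 1.5, 1.51, 1.6, 1.8, 1.99, 2.0, 2.5, 4.0) and 7 direct fractions (20, 35, 36, 49, 50, 60, 80%), which is 63 combinations. ALT took the values 1, 2.5, 2.9, 3.1, 5, 8, 8.1 and 12.

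- The action weakens with rising ALT in 4 × 5 = 20 combinations: total bilirubin 1.51 to 1.99 with direct 36% or more.
- Direct fractions of 36% and 49% also fit the isolated row's wording for a predominantly indirect rise. Without them, 4 × 3 = 12 remain; strictly above 50% direct, 4 × 2 = 8.
- Adding ALT exactly 3.0 brings in 3 × 5 = 15 more, at total bilirubin 2.0, 2.5 and 4.0, for 35 in all.

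These counts locate the fault. They are not frequencies.

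**Step 3. Is the deciding test called for?** In row (B), total bilirubin below 2.0 satisfies the condition whatever the direct fraction. Neither the row's work-up nor the panel footnote includes fractionation. If a clinician fractionates anyway, row (B) still says continue.

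**Step 4. Comparison with the protocol's own restart test.** Re-challenge in row (C) and in the isolated row requires total bilirubin below 1.5 or direct at most 35%. The row (B) patient at 1.8 and 60% fails this test for restarting at a reduced dose, yet continues at full dose.

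**Step 5. Difference in dose, expansion cohort (section 6, Table 6).** Full dose over 28 days is 400 × 28 = 11,200 mg pazopanib and 5 × 28 = 140 mg everolimus. One level lower is 200 × 28 = 5,600 mg and 5 × 14 = 70 mg. At bilirubin 1.8 and 60% direct, the ALT 2.9 patient gets nothing and then 50% if treatment resumes. The row (B) patient gets 100%.

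**Step 6. Frequency.** The documents give no rate for this cell. The nearest figure, in section 6.1.2, is concomitant transaminase and bilirubin elevations in 2 (<1%) subjects on pazopanib alone. If the denominator is the 225 subjects summarised there (an assumption), that is 2/225 = 0.9%, or 0.22 patients in 25 and 0.26 in 29, the two cohort sizes in section 14. The thresholds behind those 2 cases are not stated, so this is a guide and not a bound.

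**The case against.** Several points on the other side are sound.

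- **Row (B) is not inaction.** It requires imaging, viral serology and at least weekly liver tests that include alkaline phosphatase and GGT, whereas the isolated row names no tests and no interval. A reader might infer that the row (B) patient is dosed with no check for cholestasis. The documents do not support that: only fractionation is missing. The dosing instruction still runs the wrong way.
- **Section 6.3.1 is not wholly silent.** Its main graded rows carry "except hepatotoxicity – refer to section 6.3.3", and a reader might conclude that no other rule can apply. However, a later row for grade 3 adverse events has no such exclusion and interrupts everolimus. The documents do not give the grade 3 cut-point for ALT. If it lies between 3 and 8, that row could reach the upper part of row (B), and on that reading the 100% in step 5 would not hold for everolimus there. That row leaves pazopanib running, does not reach lower-grade ALT, and contradicts row (B). It adds a conflict and does not repair the rule.
- **The comparator is ambiguous.** Item 1 of the isolated row and row (A) both point to no change. Item 2 is the specific instruction and is taken to govern.
- **The cell is narrow.** It needs a two-sided bilirubin band, a mainly direct rise, an ALT band and no hypersensitivity symptoms, in patients enrolled with bilirubin at most 1.5 and ALT at most 2.5. The table is headed as recommendations, and section 5.6 lets treatment stop for unacceptable adverse events. This limits the severity but does not remove the reversal.

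**Conclusion.** Wrong as written; minor. Without hypersensitivity symptoms, at total bilirubin above 1.5 and below 2.0 × ULN with a mainly direct rise (clearest above 50% direct), section 6.3.3 stops both drugs at ALT below 3 and continues both at current dose at ALT above 3 and up to 8. This rests on item 2 of the isolated row governing over item 1 and row (A).

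Two stronger readings do not follow. A reader might take the 28% hyperbilirubinemia and 53% ALT elevation in section 6.1.2 as a sign that the pattern is common. Multiplied, they would give 14.8%, or about 4.3 of 29 patients. But both are any-grade rates, their independence is not shown, and pazopanib's known effect is on indirect bilirubin; the only joint figure reported is <1%. A reader might also infer that the response result is at risk. Nothing in the documents supports that, and it is not claimed here. Nor is anything drawn from the text that breaks off at the end of row (D).

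**What to change.** 1. Add to row (B): *If total bilirubin is >1.5 × ULN, fractionate. If direct is >35% and total bilirubin is <2.0 × ULN, interrupt both drugs and evaluate for cholestasis. Resume one dose level lower when total bilirubin is <1.5 × ULN or direct is ≤35%, ALT is ≤8 × ULN and not rising, there are no hypersensitivity signs, and the subject is benefiting.* Do not carry over the isolated row's ALT <3 × ULN criterion. It would keep a patient with ALT 5 and normalised bilirubin off treatment, while another with the same values and no earlier bilirubin rise continued at full dose.
2. Add direct bilirubin to the full-panel footnote whenever total bilirubin exceeds 1.5 × ULN.
3. Change the isolated row's heading to ALT ≤3.0 × ULN and make row (A) subject to it.

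With these changes the grid above, including ALT 3.0, shows no reversal (0 of 63).

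The cost is two or three lines of table text, a reflex test on blood already drawn and, for rare patients, an interruption that uses the single dose reduction allowed in the expansion cohort. The protocol already accepts that cost at lower ALT. If the team considers 1.5 to 2.0 × ULN too mild to stop for, it could raise the isolated row's stop threshold to 2.0 × ULN. That also removes the reversal, but only together with change 3, and it is the less cautious choice.
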